9.3 Interim Analyses

Interim analyses of accrued data may be conducted annually during FOURIER LEGACY study follow-up. No formal early stopping rules will be used.

10 STUDY ORGANIZATION and COMMITTEES

10.1 Study Coordination

The study is an international collaborative group study that will be coordinated by the NHMRC CTC and other RCCs.

Global statistical analysis will be performed by the NHMRC CTC in collaboration with the TIMI Study group.

10.2 Trial Executive Committee

The Study Executive Committee will oversee study planning, monitoring, progress, review of information from related research, and implementation of recommendations from other study committees and external bodies (e.g., ethics committees). The Executive Committee of the FOURIER LEGACY study will comprise of members of the FOURIER OUTCOMES Trial Executive Committee (comprising the members of the RCCs).

The Executive Committee will consider whether to continue the study as planned or modify the protocol, or stop it, based on interim analyses or other information subject to the funding agency (Amgen's) agreement.

The detailed responsibilities of the Executive Committee, its relationship with the other parties responsible for the management and conduct of the study, its membership, and the purpose and timing of its meetings will be detailed in a separate charter.

10.3 Trial Management Committee

The TMC will oversee study progress with reporting from the Executive Committee and will be involved in major decisions impacting the progress and success of the trial.

The detailed responsibilities of the TMC, its relationship with the other parties responsible for the management and conduct of the study, its membership, and the purpose and timing of its meetings will be detailed in a separate charter.

The TMC will be comprised of members of the FOURIER LEGACY Trial Executive Committee and representatives from each of the participating NCCs.

10.4 Independent Safety and Data Monitoring Committee

No ISDMC will be required, as the observational follow-up study involves no specific treatment.

The Executive Committee will review all interim analyses, in addition to other information that might influence decisions to continue the study.

11 ADMINISTRATIVE ASPECTS

11.1 Ethics and Regulatory Compliance

This study will be conducted according to ICH Good Clinical Practice 1995 (Integrated Addendum to ICH E6 (R1): Guidelines for Good Clinical Practice ICH E6(R2)) and local regulations.

The study will be conducted according to the Note for Guidance on Good Clinical Practice (CPMP/ICH/135/95) annotated with any local comments and in compliance with applicable laws and regulations in each country. The study will be performed in accordance with the principles laid down by the World Medical Assembly in the Declaration of Helsinki 2008.

To this end, no patient will be recruited to the study until all the necessary approvals have been obtained and the patient has provided written informed consent.

11.2 Confidentiality

The study will be conducted in accordance with applicable privacy acts and regulations. All data generated in this study will remain confidential. All information will be stored securely at the NHMRC CTC, University of Sydney, and will only be available to people directly involved with the study. The results of this study and a copy of the anonymised database will be provided to the TIMI Study Group and Amgen (if requested).

All regulatory requirements for protecting patient privacy, confidentiality and locally-approved methods for electronic data linkage will be complied with. All analyses will be by study ID, without patient names or other identifiers used. Strict access restrictions to all personal information will be adhered to at all times, as compatible with approvals granted for the performance of the study.

Personal data identifying trial participants will be held securely solely at each NCC for the purpose of follow-up. Storage of, and access to, pseudonymized data will be managed by the University of Sydney.

11.3 Protocol Amendments

Changes and amendments to the protocol can only be made by the Executive Committee. Approval of amendments by the Institutional HREC is required prior to their implementation. In some instances, an amendment may require a change to a consent form. The Investigator must receive approval/advice of the revised consent form prior to implementation of the change. In addition, changes to the data collected, if required, will be incorporated in the amendment.

The investigator should not implement any changes to, or deviations from, the protocol except where necessary to eliminate immediate hazard(s) to trial participant(s).

11.4 Data Handling and Record Keeping

All trial data required for the monitoring and analysis of the study will be recorded on the (e)CRFs provided. All required data entry fields must be completed. Data corrections will be done according to the instructions provided.

Source documents pertaining to the trial must be maintained by NCCs. Source documents may include a participant's medical records, hospital charts, clinic charts, the investigator's participant study files, as well as the results of diagnostic tests such as X-rays, laboratory tests, and electrocardiograms. The investigator's copy of the case report forms serves as part of the investigator's record of a participant's study-related data.

The following information should be entered into the participant's file:

- a. The participant's protocol identification.
- b. The date that the participant entered the study, and participant number.
- c. A statement that informed consent was obtained (including the date)
- d. Relevant medical history
- e. Occurrence and status of any identified Adverse Drug Reactions reportable to pharmaceutical company
- f. The date the participant exited the study, and a notation as to whether the participant completed the study or reason for discontinuation.

All study-related documentation at study sites will be maintained for at least 15 years following completion of the study.

11.5 Monitoring, Audit and Inspection

Monitoring will be in accordance with the monitoring plan. This study may be participant to inspection by representatives of the Trial Executive Committee, the funding agency Amgen, the CTC, representatives of other RCCs, or representatives of regulatory bodies.

11.6 Clinical Study Report

A Clinical Study Report which summarises and interprets all the pertinent study data collected will be issued which may form the basis of a manuscript intended for publication. The Clinical Study Report or summary thereof will be provided to the manufacturer of the study medication if requested.

11.7 Publication Policy

The Trial Executive Committee will act as the Writing Committee to draft manuscript(s) based on the trial data. Manuscript(s) will be submitted to peer-reviewed journal(s). The Writing Committee will develop a publication plan, including authorship, target journals and expected dates of publication. All manuscripts will be available prior to submission for comment from the study funder. Publication authorship will abide by the ICJME Recommendations for the Conduct, Reporting, Editing and Publication of Scholarly Work in Medical Journals.

The Executive Committee support the spirit and intent of sharing of clinical trial data.

12 PROTOCOL AMENDMENTS

Amendment No.	Date	Summary of Change
1.2	23 April 2019	
Clarification of survey question text. Section 14.1 Appendix 1. Questionnaire to Patients, question (vii) Been admitted to hospital for your heart condition?
 
Changed to (vii) Been admitted to hospital for your heart condition? (cardiovascular hospitalization is defined as hospitalization for any cardiovascular (heart or blood vessel) reason)?

1.3	18 August 2019	
Added survey question response option 'Unsure' for consistency.
 
Section 14.1 Appendix 1. Questionnaire to Patients, response to question (viii), (ix) and (x). Response options previously available (Yes/ No). This has changed to (Yes / No / Unsure)
 
Addition of Study Schema after the Synopsis
 
Addition of text to section 11.2 Confidentiality with wording about the study results and anonymised database being shared with TIMI and Amgen.
 
Addition of section 11.4 Data Handling and Record Keeping
 
Addition of section 11.6 Clinical Study Report

14 APPENDICES

14.1 Appendix 1. Questionnaire to Patients

Since you last made contact with us, have you suffered from any of the following new health events?

- (i) A new heart attack? (Y/N/Unsure)
- (ii) A new stroke? (Y/N/Unsure)
- (iii) Had one or more new coronary angioplasties (balloon treatment) or coronary stenting? (Y/N/Unsure)
- (iv) Had new coronary artery bypass surgery? (Y/N/Unsure)
- (v) Had a new angioplasty (balloon treatment) or stenting to the leg vessels? (Y/N/Unsure)
- (vi) Had an amputation of any limb (not relating to injury or accident)? (Y/N/Unsure)
- (vii) Been admitted to hospital for your heart condition (cardiovascular hospitalization is defined as hospitalization for any cardiovascular (heart or blood vessel) reason)? (Y/N/Unsure)

[For each of the above, if yes, please give month and year]

[If response is "unsure", then "thank you, we will contact you directly to help clarify your answer"]

Please also answer the following questions:

- (viii) Are you still taking a statin tablet to lower your cholesterol (you needed to be taking one to take part in the FOURIER trial)? (Y/N/Unsure)
- (ix) Are you still taking a cholesterol lowering injection (PCSK9 inhibitor drug) similar to as in the FOURIER trial (you needed to start one when you joined the FOURIER trial)? (Y/N/Unsure)
- (x) Are you taking a medication (e.g., ezetimibe or Zetia) to slow absorption of cholesterol from your diet? (Y/N/Unsure)

PLEASE INDICATE BELOW IF YOU WISH TO BE CONTACTED BY THE STUDY TEAM TO DISCUSS ANY NEW HEALTH ISSUES SINCE WE LAST CONTACTED YOU (Y/N)

Thank you very much for your participation, and for keeping us updated about your health. We will contact you again in 1 years' time to stay in touch. If you have told us that you have had one of the above health events, then we may contact you sooner, to learn more about it if necessary.

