Secondary objectives	
2. To evaluate the long-term effect of evolocumab treatment on CV death, MI and stroke.3. To evaluate the long-term effect of evolocumab treatment on CV death.4. To evaluate the long-term effects of evolocumab treatment on CHD death.5. To evaluate the long-term effect of evolocumab treatment on the individual components of the primary endpoint and any other CV hospitalizations.6. To evaluate the long-term effect of evolocumab treatment on amputations and peripheral revascularization.7. To evaluate the long-term effect of evolocumab treatment in terms of all-cause death (and non-CV, including cancer, death).
Exploratory objective	
8. To assess the effect of use of lipid-lowering treatment classes (statins, cholesterol absorption inhibitors, PCSK9i).9. To assess the effect modification by baseline characteristics on defined study outcomes above.
Design	
International multi-center observational, longitudinal follow-up study of participants who participated in the FOURIER OUTCOMES trial.

Population	
Participants in selected countries who completed the FOURIER OUTCOMES trial.

Study treatments	
None.

Assessments	
Participants will be remotely assessed (via questionnaire) upon entry into the FOURIER LEGACY study, approximately 6 and 12 months later and

[figure not shown]
then approximately annually to obtain a total of 5 years' follow-up after the date of last contact in the FOURIER OUTCOMES trial to collect details of cardiovascular hospitalizations, mortality and lipid-lowering therapy classes.

Statistical considerations

A minimum of 10,000 participants, followed over 5 years post-trial, with an assumed average post-trial event rate of 5% per annum for the primary endpoint, would have over 95% power at $2P=0.05$ to detect a 20% proportional event reduction accruing post-trial. It will also offer 80% power at $2P=0.05$ to detect a 23% reduction in CVD (from 4.94% to 3.8%).

Interim analyses of accrued data may be conducted annually post-trial as agreed from time to time by the study Steering Committee and funder. Analyses will be by intention-to-treat based on original allocated treatment in the parent FOURIER OUTCOMES trial.

Study Schema

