1 BACKGROUND

On-going and additional clinical benefits of statin therapy after trial completion have been demonstrated to accrue from a number of trials (including the 4S Study¹ and the LIPID Study^{2,3} in secondary prevention patients, and the WOSCOPS Study^{4,5} and ASCOT study⁶ in primary prevention). Furthermore, collectively in all those trials contributing to the Cholesterol Treatment Trialists' Collaboration⁷ with accessible published follow-up data, in patients who received active treatment rather than placebo over (the 3–6 years of) the original trial period, the same pattern of on-going advantage and additional risk reduction is seen.⁸ This is seen despite mostly identical usage rates of lipid-lowering therapy between the original groups for many years after completion of the trials.

In meta-analysis of the trials with accessible published post-trial data, an 8% additional reduction in total mortality at 2 years after trial close, 18% reduction in coronary mortality, and 7% reduction in total mortality and 12% reduction in coronary mortality over the next 5 years after trial close was recently reported.⁸ Collectively, these findings could have a major impact on how early initiation of lipid-lowering treatment should be considered in patients at risk. Also, because of greater emerging absolute risk differences than those apparent immediately at trial end, the net clinical benefits estimated relative to treatment costs becomes more favorable for earlier (vs deferred) intervention attributable to the original treatment assignment.

The same may or may not be true of PCSK9 inhibitor therapy, and so this needs to be examined prospectively and systematically. Similarly, in terms of potential safety issues, longer-term data after exposure provides more reliable evidence about the safety of therapy intended to be used for many years.

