2 AIM AND OBJECTIVES

The aim of this study is to determine potential long-term effects on cardiovascular outcomes of evolocumab treatment in patients enrolled in the FOURIER OUTCOMES trial through extended follow-up of selected participants beyond the treatment period.

The **primary objective** is to evaluate potential long-term effects of evolocumab treatment on a composite of CV death, MI, stroke or coronary revascularization in patients completing participation in the FOURIER OUTCOMES trial over a period of up to 5 years following completion of the FOURIER OUTCOMES trial.

The **secondary objectives**, each over a period of up to 5 years following completion of the FOURIER OUTCOMES trial, are:

1. To evaluate the long-term effect of evolocumab treatment on CV death, MI and stroke.
2. To evaluate the long-term effect of evolocumab treatment on CV death.
3. To evaluate the long-term effect of evolocumab on CHD death.
4. To evaluate the long-term effect of evolocumab treatment on the individual components of the primary endpoint and any other cardiovascular hospitalizations.
5. To evaluate the long-term effect of evolocumab treatment on amputation and peripheral revascularization.
6. To evaluate the long-term effect of evolocumab treatment in terms of all-cause death (and non-CV, including cancer, death).

Two exploratory analyses will be performed:

1. To assess effect modification of use of prescription lipid-lowering treatment classes (statins, cholesterol absorption inhibitors, PCSK9i) administered at FOURIER OUTCOMES trial entry on the outcomes above.
2. To assess the effect modification by baseline characteristics on defined study outcomes above.

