3.2 Study Enrolment

Subjects who completed the FOURIER OUTCOMES trial (defined as attendance at close-out visit irrespective of treatment compliance) will be approached by FOURIER OUTCOMES site investigators and asked about their interest in taking part in this trial. Contact details of those interested in taking part will be forwarded to the national co-ordinating center (NCC), who will contact participants to confirm consent.

Assent: Confirmation by site staff of the participant's agreement to be contacted for consent by the NCC will be provided to the NCC.

Consent: Participation will require a specific consent by each participant to allow on-going contact to be made periodically to achieve follow-up for a total of approximately 5 years from completion of the FOURIER OUTCOMES trial. Telephone consent may be acceptable if allowed by local

regulations and approved by the Ethics Committee. Additionally, approval to hold each participant's contact details (in addition to contact details for at least one relative not living with the participant) and details of treating physician(s) will be sought to facilitate reliable on-going follow-up, and signed authorization for study staff to seek supplementary information and source documentation about health events will be collected. Participants will provide details of the preferred mode of communication (SMS, email, letter, phone) at the time of consent. Personal data identifying trial participants will be held securely solely at each NCC for the purpose of follow-up.

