5.2 Details of Assessments

Participants will be contacted upon entry into the FOURIER LEGACY study, and then approximately 6 months later. Following this, contact will be made approximately annually to obtain follow-up for a total of 5 years after the date of last contact in the FOURIER OUTCOMES trial. Each participant will be sent a unique link to a secure website and asked to provide details of any cardiovascular events and lipid-lowering therapy classes used since the last contact (Appendix 1 lists data to be collected). A proportion of events will be adjudicated as detailed in Section 8.1.

Participants will be contacted directly (by their preferred method of communication) or via a proxy, as agreed and in accordance with local regulations.

Participants who do not complete the required information despite reminders will be contacted directly by the relevant NCC.

Where permitted by local regulations, permission will be sought to collect data from any available national/local registries.

All consenting participants are expected to be followed up to the end of the study. All efforts must be made to maintain follow-up per the visit schedule. If this is not possible, follow-up should still occur wherever possible via periodic contact, the participant's other nominated contacts, their usual doctors, contact at study closure and any available national/local registries, as permitted by local regulations.

To ensure no bias is introduced into the assessment of possible late safety signals from prior evolocumab treatment in the FOURIER OUTCOMES trial, every effort will be made to ascertain causes of death for participants who may have died since the FOURIER OUTCOMES trial close-out and prior to the commencement of this study.

5.3 *Withdrawal From Contact or From Follow-up*

Withdrawal from on-going contact by the designated NCC may occur at any time by participant request, with confirmation to be documented clearly. Withdrawal of consent should only occur if the participant refuses any further assessments or contact whatsoever. Any data collected prior to a participant's withdrawal of consent will be maintained in the database and analyzed.

It is expected that all options for continued participation are explained to the participant and the reason for refusal is documented.

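### The entry questionnaire does not tie its look-back to the last FOURIER OUTCOMES contact, so non-fatal events between close-out and LEGACY entry may go unreported although they fall in the 5-year window

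*Protocol*

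**What the plan says.** **Window.** Section 2 sets the primary objective "over a period of up to 5 years following completion of the FOURIER OUTCOMES trial". Section 5.2 schedules contacts "to obtain follow-up for a total of 5 years after the date of last contact in the FOURIER OUTCOMES trial". The time between close-out of the parent trial and entry into LEGACY is therefore inside the window.

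**Instrument.** The Synopsis states: "Participants will be remotely assessed (via questionnaire) upon entry into the FOURIER LEGACY study". One form is shown, in Appendix 1 (Section 14.1), and its stem reads: "Since you last made contact with us, have you suffered from any of the following new health events". Section 5.2 describes the same task: participants are "asked to provide details of any cardiovascular events and lipid-lowering therapy classes used since the last contact". Neither place says which contact is meant at entry.

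**Order of contacts.** Under Section 3.2 the parent-trial site first approaches the participant. Then: "Contact details of those interested in taking part will be forwarded to the national co-ordinating center (NCC), who will contact participants to confirm consent". Section 3.2.1 places signed consent before registration and participation.

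**The interval before entry.** Section 5.2 promises every effort to establish causes of death for people who died between close-out and the start of LEGACY. It has no matching sentence for non-fatal events.

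**The concern.** MI, stroke and coronary revascularization are components of the primary endpoint. If a participant takes the last contact to be the consent call, a heart attack or stent after close-out but before that call is correctly answered with a no. On the form, only an answer of unsure triggers a clarifying contact. Later forms look back to the preceding contact, so they do not ask about the event again.

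Person-time from close-out would then count while some non-fatal events in it would not. Early post-trial rates would be too low, and the recorded first post-trial event would in some participants be a later one. The analyses of the post-close trajectory in Section 9.2 (landmark and conditional probability plots) would be affected most, because they depend on when events occur after close-out. Fewer recorded events would also reduce power below what Section 9.1 assumes.

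**Working it through.** **1. Reading the passages together**

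| Question | What the protocol gives |
|---|---|
| When does the window start? | Last contact in FOURIER OUTCOMES (5.2) |
| When does the entry look-back start? | Last contact, not further defined (5.2, 14.1) |
| Which contacts come before the entry form? | Site approach, then the consent contact (3.2) |
| What retrieval is specific to the gap? | Causes of death only (5.2) |
| Is the form adapted to entry? | It appears not: its closing line announces the next contact in a year, whereas 5.2 puts the contact after entry at about 6 months |

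The start of the window is defined and the start of the entry look-back is not.

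**2. Reproducing the stated power**

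Inputs from Section 9.1: 10,000 participants, 5 years, 5% per year, two-sided 0.05. Assumptions: 5% is the rate in the former placebo arm, 5,000 per arm (the ratio in this cohort is not stated), exponential event times, no dropout.

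First events over T years: d(T) = 5,000 × [(1 − e^(−0.05T)) + (1 − e^(−0.05·HR·T))]

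Power: Φ(½√d × |ln HR| − 1.96)

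- HR 0.85, T = 5: d = 5,000 × (0.2212 + 0.1914) = 2,063. Power = Φ(22.71 × 0.1625 − 1.96) = Φ(1.73) = 95.8%. Section 9.1 states over 90%.
- HR 0.80, T = 5: d = 2,012, power 99.9%. Section 9.1 states over 95%.

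Both stated figures are confirmed.

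**3. Upper bound on the loss**

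The protocol does not give the time from close-out to entry. I take 1 and 2 years as an assumed range and suppose that every primary event in the gap is lost. There are two ways to count what remains:

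- *A, subtract:* d = d(5) − d(g). A participant with a gap event contributes no later event.
- *B, restart:* d = d(5 − g). All 10,000 count as event-free at entry, so a later event can be recorded as the first.

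| HR | Gap | Events in gap, d(g) | A: events, power | B: events, power |
|---|---|---|---|---|
| 0.85 | 0 | 0 | 2,063, 95.8% | 2,063, 95.8% |
| 0.85 | 1 year | 452 (22% of 2,063) | 1,611, 90.4% | 1,688, 91.6% |
| 0.85 | 2 years | 883 (43% of 2,063) | 1,180, 79.7% | 1,295, 83.3% |
| 0.80 | 2 years | 860 (43% of 2,012) | 1,152, 96.6% | 1,262, 97.7% |

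Power of 90% at HR 0.85 needs 4 × (1.960 + 1.282)² / (ln 0.85)² = 42.03 / 0.02641 = about 1,591 events. Under A that number is lost at a gap of about 1.05 years (2,063 − 472 = 1,591). Under B it is lost at about 1.25 years (d(3.75) = 1,591). So the stated power for a 15% reduction fails only if the gap is longer than about a year and the loss is complete.

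The table is an upper bound for two reasons. It removes cardiovascular deaths along with non-fatal events, although causes of death in the gap are pursued separately. It also credits nothing to registries or other sources.

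**The case against.** The strongest reply is that Section 5.2 supplies the anchor. It counts follow-up from the last FOURIER OUTCOMES contact and, in the next sentence, asks for events since the last contact. Read together, at entry that contact is the FOURIER one. Continuity supports this: parent-trial sites make the approach, participants keep their FOURIER ID, and an entry form covering only the time since consent would have little purpose. This reading is open, so a reader who infers that the anchor *is* the consent contact goes further than the text. But participants see the form and not Section 5.2, and the form neither gives a date nor says that contact with the FOURIER trial counts. Two readings are enough for participants to answer differently.

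A second reply is that other sources exist: registries where permitted, direct contact with non-responders, usual doctors when scheduled follow-up fails, and authorization to seek source documents. That stands against any inference that gap events are never recovered. It does not close the gap, because none of these is directed at a participant who returns the form with a no.

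A third reply is that the sentence on deaths exists because people who have died cannot answer a form, so its silence on non-fatal events does not show an intention to omit them. That is fair. The sentence shows only that the gap was foreseen and that no equivalent was written for non-fatal events.

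A reader might also infer that the lost stretch is where the legacy effect is largest, since Section 1 cites "an 8% additional reduction in total mortality at 2 years after trial close, 18% reduction in coronary mortality", against 12% over 5 years. Those figures are for coronary mortality. The events at risk here are non-fatal, and causes of death in the gap are the one thing Section 5.2 does pursue. The comparison does not bear on this point.

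**Conclusion.** The entry look-back is undefined, and a natural reading of the form leaves out part of the primary-endpoint window. This is a real weakness in the instrument. It does not prove that events were missed.

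Both arms receive the same form, and the documents show no reason for differential reporting, so a biased comparison between arms is not established. What is at stake is fewer events, early rates that are too low and wrong first-event dates. If every gap event were lost, power for a 15% reduction would fall from 95.8% to about 90–92% at a 1-year gap and 80–83% at 2 years. Power for a 20% reduction would stay above 95% for gaps up to 2 years. These figures rest on the protocol's 5% per year and 10,000 participants, an assumed 1:1 split, and an assumed gap length. The true loss is probably smaller and cannot be determined from the protocol.

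**What to change.** - **Entry form:** word the stem *Since your last visit in the FOURIER trial on [pre-filled date]*.
- **Later forms:** pre-fill the date of the last completed questionnaire.
- **Section 5.2:** say that the look-back runs from the last FOURIER OUTCOMES contact on the entry questionnaire and from the last completed questionnaire afterwards.
- **Participants who have already answered the present entry form:** put the FOURIER-dated question to them once, at their next contact.

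The cost is a wording amendment with the ethics approval that Section 11.3 requires, and one pre-filled field. The last-contact date should come from the parent database, which Section 9.2 already brings into the follow-up database. The downside is a longer recall period at entry, with less certain event dates. That is preferable to leaving participants to guess the period asked about.
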